The molecular mechanism of thyroid carcinogenesis and progression is the abnormal activation of intracellular signal transduction induced by related gene changes. Among these, MAPK signaling pathway is one of the important signaling pathways for thyroid carcinogenesis and progression. The missense mutation of a single base in Exon 15 of BRAF gene (GTG>GAG) causes the replacement of valine (V) corresponding to codon 600 of translation protein by glutamate (E), which becomes activated protein kinase, and induces tumor formation by activating MAPK signaling pathway. TERT promoter mutation induces the abnormal activation of telomerase, which is a key step in thyroid carcinogenesis. It has been found that ETS (E-twenty-six) protein is a transcription factor family downstream of the BRAF-MAPK signaling pathway. When TERT gene promoter mutates, it can produce some special nucleotide sequences, which can bind to ETS protein, and cause tumorigenesis by enhancing TERT gene expression. Many studies have shown that BRAF gene V600E mutation and two mutations in TERT gene promoter region (1 295 228C>T and 1 295 250C>T) are frequently observed in thyroid cancer, and the poor prognosis of thyroid cancer patients can be effectively evaluated. Further studies have confirmed that the coexistence of BRAF and TERT promoter mutations has a synergistic effect on the invasiveness of thyroid cancer, and the two mutated tumors

are related to the high recurrence risk and increased disease-specific mortality of differentiated thyroid cancer, as well as a higher mortality trend in ATC. Therefore, TERT promoter mutation and BRAF mutation can be used as molecular markers for thyroid diagnosis.

TERT promoter mutation and BRAF mutation are closely related to clinical evaluations such as preoperative diagnosis and prognostic risk assessment of thyroid cancer, which have been clearly described in relevant guidelines. The NCCN Clinical Guidelines (Thyroid Cancer) - 2018 V3 Edition, the World Health Organization (WHO) Endocrine Tumors 2017 V4 Edition, the ATA Management Guidelines for Thyroid Nodules and Anaplastic Thyroid Cancer 2015 Edition, the Expert Consensus on Diagnosis and Treatment of Thyroid Micropapillary Carcinoma, and the Chinese Society of Clinical Oncology (CSCO) Guidelines for Diagnosis and Treatment of Persistent/Recurrent and Metastatic Thyroid Cancer in 2018 V1 Edition pointed out that, TERT promoter mutation or BRAF gene mutation showed high mutation frequency in thyroid tissue, and predicted benign and malignant tumors and adverse prognosis of patients. Among these, the ATA Management Guidelines for Thyroid Nodules and Anaplastic Thyroid Cancer 2015 Edition and the Expert Consensus on Diagnosis and Treatment of Thyroid Micropapillary Carcinoma clearly pointed out that, benign and malignant thyroid tumors cannot be determined by fine needle biopsy, and the detection of BRAF mutation and TERT promoter mutation gene can be carried out on punctured specimens, which is helpful to improve the diagnosis rate. In addition, CSCO guidelines point out that, BRAF gene mutation and TERT gene promoter mutation are not only poor prognostic indicators for patients with thyroid cancer, but also have a greater impact on the absorption of radioactivity I in PTC patients. For PTC patients with distant metastasis, the pre-detection of BRAF V600E and other gene mutations is helpful for predicting the ¹³¹I uptake, therapeutic effect and prognosis of patients with distant metastasis. Moreover, the targeted drug dabrafenib plus trametinib can effectively alleviate ATC with BRAF mutation, while for ¹³¹I-resistant patients with BRAF mutation, dabrafenib plus ¹³¹I can restore the absorption of ¹³¹I in some patients. Therefore, the detection of TERT promoter and

BRAF gene mutation is helpful for the diagnosis and clinical prognosis prediction of thyroid cancer, and convenient for making individualized diagnosis and treatment options.

The Genetron TERT/BRAF PCR Kit is used to qualitatively detect two mutations in the TERT gene promoter region (1295 2228C > T and 1295 250C > T) and BRAF gene V600E mutation (GTG > GAG) within the DNA of thyroid nodule histiocytes obtained by fine needle aspiration (FNA). Assisted fine needle biopsy is used in the diagnosis of benign and malignant thyroid nodules.

2 Study Purpose

The purpose of this study is to evaluate the detection performance of the Genetron TERT/BRAF PCR Kit (PCR-fluorescence probe method) by comparing the results of this kit to those of the simultaneous detection with Sanger sequencing method. Meanwhile, the clinical diagnosis performance of the Genetron TERT/BRAF PCR Kit (PCR-fluorescence probe method) will also be evaluated by comparing the results of this kit to the clinical reference standard (pathological findings or clinical diagnosis conclusions). By combining both evaluations, the intended use of the kit and the detection accuracy of the analyte can be comprehensively evaluated.

3 Study Design

3.1 Overall Study Design

3.1.1 Detection performance validation of test reagent

This trial will be conducted in accordance with the principles of the synchronous blind method. The selected cases will be coded, and the selected samples will be detected with the test reagent and comparison method (Sanger sequencing). When the comparison results are inconsistent with the detection results of Sanger sequencing method, the detection results of sanger will be acceptable.

3.1.2 Performance validation of test reagent

Among the enrolled patients, postoperative pathological results will be obtained from those who underwent surgery subsequently. Those with pathologically confirmed thyroid cancer will be considered as positive, while those without pathologically

confirmed thyroid cancer whose clinical diagnosis is non-cancer without surgery will be considered as negative. The results of the test reagents will be compared and the clinical sensitivity and specificity of the test reagents will be calculated.

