3.2.1.2 Sample Size of Diagnostic Performance Verification

$$n = \frac{\left[Z_{1-\alpha/2} \sqrt{P_0(1-P_0)} + Z_{1-\beta} \sqrt{P_T(1-P_T)} \right]^2}{(P_T - P_0)^2}$$

Where, n represents the sample size; $Z_{1-\alpha/2}$ and $Z_{1-\beta}$ are fractions of standard normal distribution, P_0 is the target value of the evaluation indicator, and P_T is

the expected value of the evaluation indicator for in vitro diagnostic reagents.

Samples with BRAF or TERT mutation detected by the test reagent are considered as positive, and samples without mutation are considered as negative.

The results of pathological examination and clinical diagnosis will be used for comparison method. Those with pathologically confirmed thyroid cancer will be considered as positive, while those without pathologically confirmed thyroid cancer whose clinical diagnosis is non-cancer without surgery will be considered as negative.

According to relevant literature reports and preclinical study results, if the target value of sensitivity for the test reagent and comparison method is up to 50% with the expected value up to 60%, the minimum sample size of positive control group is estimated to be 194. According to previous experience, the proportion of positive diagnosis upon postoperative pathological examination is generally more than 70%. If estimated as 70%, the overall sample size of prospectively enrolled patients is 278. The target specificity value is 80% with the expected value of 90%, the minimum sample size of negative control group is estimated to be 108. If the proportion of negative results obtained from the postoperative pathological examination is estimated as 30%, the overall sample size of prospectively enrolled patients is 360. For the final overall sample size calculated based on sensitivity and specificity, the larger one (360 cases) shall prevail. Considering the estimated dropout rate of 10%, the final actual overall sample size is 400.

It is planned to carry out the trial in at least three clinical sites, with the enrollment of no less than 300 samples at each site. In case of objective reasons, when the sample size is insufficient, appropriate adjustments can be made among the sites to ensure the overall sample size. If the relevant laws and regulations change during the trial, the latest laws and regulations shall prevail, and the number of samples should be statistically significant.

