3.2.4 Sample numbering

In principle, only one sample should be collected from one subject, and each enrolled sample of the two detection methods should have a unique clinical trial number (secondary code). After sample enrollment, before sample detection, the blinding personnel will mark the secondary code outside the DNA sample tubes according to the blinding table, prepare the Blinding Records and carefully record the comparison table between the primary code (subject enrollment number) and the secondary code as the blind codes. Blinding documents shall be kept independently by the blinding

personnel until breaking of blindness.

During experimental procedures, only the secondary code of samples is reflected.

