4.3 Positive, Negative and Total Coincidence Rates Between Test Reagent and Comparison Method

For each genetic locus, fourfold tables will be used to calculate the positive and negative coincidence rates, positive and negative predictive values, total coincidence rate and their 95% confidence intervals. Using statistical software, Kappa test is used to determine statistical significance of the two methods.

Table 1 Result Summary of Clinical Trial Comparing Test Reagent and Comparison Method

Test Reagent	Comparison Method		Total
	Positive	Negative	
Positive	A	B	A+B
Negative	C	D	C+D
Total	A+C	B+D	A+B+C+D

Samples with mutant genotype detected are considered as positive, and samples without mutant genotype are considered as negative.

The calculation formula is:

$$\text{Positive coincidence rate} = A/(A+C) \times 100\%$$

$$\text{Negative compliance rate} = D/(B+D) \times 100\%$$

$$\text{Positive predictive value (PPV)} = A/(A+B) \times 100\%$$

$$\text{Negative predictive value (NPV)} = D/(C+D) \times 100\%$$

$$\text{Total coincidence rate} = (A+D)/(A+B+C+D) \times 100\%$$

The calculation formula of 95% confidence interval: $p \pm 1.96 \times [p(1-p)/n]^{1/2}$ (where P represents positive and negative coincidence rates, positive and negative predictive values and total coincidence rate, n presents the sample size. If $p > 0.9$, Wilson score method will be used for correction).

4.4 Sensitivity, Specificity and Total Coincidence Rate of Test Reagent and Clinical Reference Standard

Table 2 Result Summary of Test Reagent and Clinical Reference Standard

Test Reagent	Gold standard		Total
	Positive	Negative	
Positive	A (true-positive)	B (false-positive)	A+B
Negative	C (false-negative)	D (true-negative)	C+D
Total	A+C	B+D	A+B+C+D

Those with pathologically confirmed thyroid cancer will be considered as positive, while those without pathologically confirmed thyroid cancer whose FNA result is non-cancer without surgery will be considered as negative.

The test reagent and comparison method will be compared, but patients who fail to provide follow-up pathological results will not be included in the comparative

statistics of test reagent and clinical reference standard.

The calculation formula is:

$$\text{Sensitivity} = A/(A+C) \times 100\%$$

$$\text{Specificity} = D/(B+D) \times 100\%$$

$$\text{Total coincidence rate} = (A+D)/(A+B+C+D) \times 100\%$$

$$\text{Positive predictive value (PPV)} = A/(A+B) \times 100\%$$

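### The reference standard classifies the patient, the kit classifies one aspirated nodule, and nothing requires the confirmed cancer to lie in that nodule

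*Protocol*

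**What the plan says.** **Reference standard (patient).** Section 3.1.2 starts from patients: "Among the enrolled patients, postoperative pathological results will be obtained from those who underwent surgery subsequently". It then classifies them: "Those with pathologically confirmed thyroid cancer will be considered as positive". Section 3.2.1.2 repeats this rule. Section 4.4 gives it again, with the FNA result in place of the clinical diagnosis for the negative side: "Those with pathologically confirmed thyroid cancer will be considered as positive, while those without pathologically confirmed thyroid cancer whose FNA result is non-cancer without surgery".

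**Kit result (sample).** Section 3.2.1.2: "Samples with BRAF or TERT mutation detected by the test reagent are considered as positive, and samples without mutation are considered as negative". Section 3.2.4: "In principle, only one sample should be collected from one subject".

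**Intended use (nodule).** The paragraph just before section 2 states: "Assisted fine needle biopsy is used in the diagnosis of benign and malignant thyroid nodules".

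The inclusion, exclusion and elimination criteria (3.2.2.1 to 3.2.2.3) do not restrict enrolment to single nodules and do not remove patients whose cancer is outside the sampled nodule. The clinical information listed in 3.2.2.1 does not name nodule location.

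**The concern.** The two margins of Table 2 in section 4.4 have different units: the rows describe a nodule and the columns a patient. They agree when the aspirated nodule is the cancer, or when the gland holds no cancer. They disagree when the aspirated nodule is benign and the resected gland contains cancer elsewhere. The written rule then does one of two things:

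- If the nodule has no mutation, the kit was right, but the patient enters cell C as a false negative. This lowers sensitivity and NPV.
- If the kit calls a mutation in the benign nodule, the patient enters cell A as a true positive. This hides a false positive and raises PPV.

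Kappa (section 4.5) uses the same cells. At stake is whether these figures describe the nodule-level use that the kit is meant for, and whether the sensitivity criterion in section 4.6 is judged on a diluted estimate. The definition of the reference standard is fixed in the protocol, in three places, so it is not a detail left open for an analysis plan.

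**Working it through.** **Inputs from protocol section 3.2.1.2.** Sensitivity: target 50%, expected 60%, 194 positives. Specificity: target 80%, expected 90%, 108 negatives. Share positive at postoperative pathology: 70%. Dropout: 10%. Section 4.1 gives two-sided tests at 0.05. Power is not stated; 80% is assumed because it reproduces the protocol's numbers.

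**Reproducing the plan.** The formula is n = [z(1−α/2)·√(P0(1−P0)) + z(1−β)·√(PT(1−PT))]² / (PT−P0)².

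- Sensitivity: [1.96·√0.25 + 0.8416·√0.24]² / 0.10² = 193.85, so 194.
- Specificity: the same formula with 0.80 and 0.90 gives 107.43, so 108.
- Enrolment: 194/0.70 = 277.1, so 278; 108/0.30 = 360; 360/0.90 = 400.

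All agree with the protocol. The larger requirement, 360, governs, so the planned number of positives is 0.70 × 360 = 252, and 194 is only the minimum.

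**Effect of the mismatch.** Let m be the share of reference-positive patients whose cancer lies only outside the aspirated nodule. No section gives m, so it is an assumption shown over a range. Two further assumptions are needed: the expected 60% is nodule-level, and a benign nodule tests positive 10% of the time (1 minus the expected specificity of 90%). Then

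observed sensitivity = 0.60(1−m) + 0.10m.

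- m = 2%: 0.588 + 0.002 = 59.0%
- m = 5%: 0.570 + 0.005 = 57.5%
- m = 10%: 0.540 + 0.010 = 55.0%
- m = 20%: 0.480 + 0.020 = 50.0%, equal to the target

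**Chance of meeting the criterion.** Section 4.6 is read as requiring a lower 95% limit for sensitivity above 50%. The limit is the one in section 4.4, p − 1.96·√(p(1−p)/n); its Wilson variant applies only above 90%. With n = 252, at least 142 positives are needed: 142/252 = 56.3%, lower limit 50.2%. With n = 194, at least 111 are needed: 57.2%, lower limit 50.3%. Exact binomial probabilities of reaching these counts:

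| m | Observed sensitivity | 194 positives | 252 positives | 567 positives |
|---|---|---|---|---|
| 0 | 60.0% | 81% | 89% | 99.8% |
| 2% | 59.0% | 72% | 82% | 99% |
| 5% | 57.5% | 56% | 67% | 95% |
| 10% | 55.0% | 29% | 36% | 67% |

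The last column takes the other enrolment figure in section 3.2.1.2, at least 300 samples at each of at least three sites: 900 × 0.90 × 0.70 = 567. The protocol does not reconcile that figure with 400. More patients reduce the loss of power, but the expected estimate stays at 57.5% for m = 5% at any n.

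**The case against.** The strongest reply is that the protocol never says a cancer anywhere in the gland counts. Inclusion criterion (2) lists the pathological diagnosis among the information each sample must have, and for unoperated patients section 4.4 uses the FNA result, which belongs to the punctured nodule. A lesion-level reading is therefore open. This stands as far as it goes: it shows that sites could match nodules, not that they must. Section 3.1.2 starts from enrolled patients, and no section asks for correspondence. With at least three sites, practice may differ.

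Several other points stand and limit the size:

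- m is in no section and may be small.
- The 60% rests on literature and preclinical results whose unit is not shown. If they were patient-level, the dilution is already in the 60%, and the formula above would subtract it twice.
- The net effect on sensitivity is downward, so on that criterion the mismatch does not help the kit pass. PPV can move the other way.

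A reader might also infer that the planned 108 negatives will be short because benign nodules move to the positive group. The documents do not support this: the 70/30 split refers to postoperative pathology results and may already be patient-level, in which case 108 is the number left after any such move. Nor is a bias in specificity itself shown.

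**Conclusion.** The mismatch of units is in the text and holds: a patient-level reference is set against a nodule-level test, with no rule linking the two. As written, it misclassifies benign aspirated nodules in patients with cancer only elsewhere, and sensitivity, PPV, NPV and kappa then no longer describe the nodule.

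The size is conditional. At the planned 252 positives, and if the 60% is nodule-level with 10% of benign nodules testing positive, an m of 5% would cost 2.5 percentage points of sensitivity and 22 points of power (89% to 67%). The cost is larger at the minimum of 194, smaller if three sites each enrol 300, and already included if the 60% is patient-level.

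A reader might conclude that the sensitivity criterion is likely to fail. The documents do not support that, because they give no value for m. They support only that the rule should be corrected and that, without recorded nodule location, the sponsor may be unable to show afterwards that the effect was small.

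**What to change.** In protocol sections 3.1.2, 3.2.1.2 and 4.4:

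1. Define reference-positive as cancer confirmed by pathology in the aspirated nodule, matched by side, location and size between the FNA record and the surgical pathology report.
2. Classify a pathologically benign aspirated nodule with cancer only elsewhere in the gland as reference-negative. State this expressly, because these patients had surgery and the present negative rule refers to patients without surgery.
3. Prespecify how cases that cannot be matched are handled.
4. Report the patient-level classification as a sensitivity analysis.
5. State whether the expected 60% sensitivity and the 70% positive share are nodule-level or patient-level.

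The cost is protocol wording and one nodule-location field on the case report form, filled from existing FNA and pathology reports. A few patients may remain unmatched. No extra sample or procedure is needed.

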3.2 Sample Screening

3.2.1 Basis to Determine Sample and Sample Size

3.2.1.1 Sample Size of Test Performance Verification

$$n = \frac{\left[Z_{1-\alpha/2} \sqrt{P_0(1-P_0)} + Z_{1-\beta} \sqrt{P_T(1-P_T)} \right]^2}{(P_T - P_0)^2}$$

Where, n represents the sample size; $Z_{1-\alpha/2}$ and $Z_{1-\beta}$ are fractions of standard normal distribution, P_0 is the target value of the evaluation indicator, and P_T is the expected value of the evaluation indicator for in vitro diagnostic reagents.

- (1) BRAF gene: According to the results of preclinical studies, the target value of positive coincidence rate between test reagent and contrast reagent is up to 85% with the expected value up to 95%, the minimum sample size of positive control group is estimated to be 78; the target value of negative coincidence rate is up to 85% with the expected value up to 90%, the minimum sample size of negative control group is estimated to be 363 and the minimum overall sample size is 441.
- (2) TERT gene: According to the results of preclinical studies, the target value of positive coincidence rate between test reagent and contrast reagent is up to 85% with the expected value up to 98%, the minimum sample size of positive control group is estimated to be 40; the target value of negative coincidence rate is up to 85% with the expected value up to 90%, the minimum sample size of negative control group is estimated to be 363 and the minimum overall sample size is 403.

3.2.1.2 Sample Size of Diagnostic Performance Verification

$$n = \frac{\left[Z_{1-\alpha/2} \sqrt{P_0(1-P_0)} + Z_{1-\beta} \sqrt{P_T(1-P_T)} \right]^2}{(P_T - P_0)^2}$$

Where, n represents the sample size; $Z_{1-\alpha/2}$ and $Z_{1-\beta}$ are fractions of standard normal distribution, P_0 is the target value of the evaluation indicator, and P_T is

the expected value of the evaluation indicator for in vitro diagnostic reagents.

Samples with BRAF or TERT mutation detected by the test reagent are considered as positive, and samples without mutation are considered as negative.

The results of pathological examination and clinical diagnosis will be used for comparison method. Those with pathologically confirmed thyroid cancer will be considered as positive, while those without pathologically confirmed thyroid cancer whose clinical diagnosis is non-cancer without surgery will be considered as negative.

According to relevant literature reports and preclinical study results, if the target value of sensitivity for the test reagent and comparison method is up to 50% with the expected value up to 60%, the minimum sample size of positive control group is estimated to be 194. According to previous experience, the proportion of positive diagnosis upon postoperative pathological examination is generally more than 70%. If estimated as 70%, the overall sample size of prospectively enrolled patients is 278. The target specificity value is 80% with the expected value of 90%, the minimum sample size of negative control group is estimated to be 108. If the proportion of negative results obtained from the postoperative pathological examination is estimated as 30%, the overall sample size of prospectively enrolled patients is 360. For the final overall sample size calculated based on sensitivity and specificity, the larger one (360 cases) shall prevail. Considering the estimated dropout rate of 10%, the final actual overall sample size is 400.

It is planned to carry out the trial in at least three clinical sites, with the enrollment of no less than 300 samples at each site. In case of objective reasons, when the sample size is insufficient, appropriate adjustments can be made among the sites to ensure the overall sample size. If the relevant laws and regulations change during the trial, the latest laws and regulations shall prevail, and the number of samples should be statistically significant.

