4.1 General Principles of Statistical Analysis

SAS 9.4 or above software will be used for statistical analysis. The sample size is calculated with PASS16. The statistical analysis of the validity and accuracy of test results is based on full analysis set (FAS) and per protocol set (PPS), and the safety analysis is based on safety set (SS). All statistical tests will be conducted on both sides and $P \leq 0.05$ will be considered statistically significant. (Unless otherwise specified)

The quantitative variables are expressed as mean, standard deviation, median, minimum, maximum, lower quartile (Q1) and upper quartile (Q3), while the categorical variables are expressed as the number and percentage of each category.

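### The clinical sample size applies a positive/negative split seen in operated patients to all enrolled FNA patients, with no surgery rate, so the 194 positives depend on an unstated assumption

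*Protocol*

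**What the plan says.** Protocol section 3.2.1.2 sizes the clinical comparison in three steps.

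- **Group sizes.** For sensitivity, the target "is up to 50% with the expected value up to 60%, the minimum sample size of positive control group is estimated to be 194". For specificity: "The target specificity value is 80% with the expected value of 90%, the minimum sample size of negative control group is estimated to be 108".
- **Totals.** The positive share is described as that found at postoperative pathology, generally above 70%. The section continues: "If estimated as 70%, the overall sample size of prospectively enrolled patients is 278". The negative share, also from postoperative pathology, is put at 30%, which gives 360 enrolled.
- **Final number.** The larger total, 360, is raised for 10% dropout to 400, which the section calls the final overall sample size. The next paragraph plans at least three sites with at least 300 samples each.

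Enrolment (3.2.2.1) is of patients with suspected thyroid cancer who had FNA. Surgery is not a criterion. Section 3.1.2 says that "postoperative pathological results will be obtained from those who underwent surgery subsequently".

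A reference positive is a cancer confirmed by pathology. Sections 3.1.2 and 3.2.1.2 count unoperated patients with a clinical diagnosis of non-cancer as reference negatives. Section 4.4 does the same on the basis of the FNA result, but then adds that "patients who fail to provide follow-up pathological results will not be included in the comparative" statistics against the clinical reference standard.

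**The concern.** The 70% and 30% are shares of patients with postoperative pathology. Dividing a group size by such a share gives the number of operated patients needed, not the number to enrol. The step from one to the other needs the proportion of enrolled patients who go on to surgery, and the protocol gives none. The only allowance is 10% for dropout.

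Section 4.6 makes the lower 95% confidence limits against the 50% and 80% targets the pass/fail test of diagnostic accuracy. Too few patients with the required reference result would lower the chance of meeting a criterion that the product might truly satisfy.

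**Working it through.** **Inputs.** The formula and the target and expected values come from 3.2.1.2. The two-sided 5% level comes from 4.1. Power is not stated; 80% is assumed because it reproduces the stated group sizes (90% would give 259 and 137).

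**The plan's own figures.** With n = [1.96·√(P0(1−P0)) + 0.8416·√(PT(1−PT))]² / (PT−P0)²:

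- Sensitivity, 0.50 against 0.60: (0.980 + 0.412)² / 0.01 = 193.8, so 194.
- Specificity, 0.80 against 0.90: (0.784 + 0.252)² / 0.01 = 107.4, so 108.
- 194/0.7 = 277.1, so 278; 108/0.3 = 360; 360/0.9 = 400.

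Every stated figure reproduces.

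**Adding the surgery rate.** Let f be the fraction of enrolled patients who have surgery with pathology. The protocol does not give f, so a range is shown. Among 400 enrolled:

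- positives = 0.7 × 400f = 280f
- pathology-verified negatives = 0.3 × 400f = 120f
- negatives including unoperated patients, if all of these are judged non-cancer = 120f + 400(1−f) = 400 − 280f

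Power = Φ{[(PT−P0)√n − 1.96·√(P0(1−P0))] / √(PT(1−PT))}.

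| f | Positives | Sensitivity power | Pathology-verified negatives | Specificity power | Negatives incl. unoperated | Specificity power |
|---|---|---|---|---|---|---|
| 0.9 | 252 | 89.3% | 108 | 80.3% | 148 | 92.5% |
| 0.8 | 224 | 85.4% | 96 | 74.3% | 176 | 96.5% |
| 0.7 | 196 | 80.4% | 84 | 67.1% | 204 | 98.4% |
| 0.6 | 168 | 74.1% | 72 | 58.5% | 232 | 99.3% |
| 0.5 | 140 | 66.1% | 60 | 48.8% | 260 | 99.7% |

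**Surgery rate needed for the stated group sizes.**

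| Patients | 194 positives | 108 pathology-verified negatives |
|---|---|---|
| 400 | 194/280 = 69% | 108/120 = 90% |
| 360 (400 less a separate 10% dropout) | 194/252 = 77% | 108/108 = 100% |
| 900 (3 × 300) | 194/630 = 31% | 108/270 = 40% |
| 810 (900 less 10%) | 194/567 = 34% | 108/243 = 44% |

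When unoperated non-cancers count, negatives are lowest at f = 1: 400 − 280 = 120, or 360 − 252 = 108 after dropout. They never fall below 108.

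**Enrolment with f included.** Total = group size / (class share × f × 0.9). At f = 0.7, positives need 194/(0.7 × 0.7 × 0.9) = 440 and pathology-verified negatives need 108/(0.3 × 0.7 × 0.9) = 572. At f = 0.5 the totals are 616 and 800.

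**The case against.** The strongest reply is that the protocol nowhere requires the 108 negatives to be verified by pathology. Sections 3.1.2, 3.2.1.2 and 4.4 all admit unoperated patients judged non-cancer, and on that rule specificity is more than adequately powered. The exclusion in 4.4 can be read as covering only patients lost to follow-up. This stands. A reader might infer that the plan works only if about 90% of patients have surgery; the documents do not support that as a general statement. It follows only if the 4.4 exclusion is applied literally to unoperated patients, which contradicts the negative definition just before it. The reply does not rescue the calculation, though. If unoperated patients count, the negative share among those enrolled is not 30%, and 360, the figure that sets the total, has no basis.

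A reader might also infer that power is lost whichever rule applies. That is not so: with unoperated non-cancers counted, nothing is lost once f reaches about 69% (77% with separate dropout).

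The site minimum is a second good reply. At 900 enrolled, much lower surgery rates suffice. But 3.2.1.2 calls 400 the final number, allows adjustment among sites to secure the overall sample size, and does not link the 900 to surgery uptake. The site minimum reduces the practical risk without correcting the derivation.

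Finally, 3.2.2.1 lists pathological diagnosis among the required sample information and 3.2.2.3 removes incomplete samples, so 360 might be meant as patients with a usable result. The wording could equally mean cytology, and the totals are explicitly labelled as enrolled.

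**Conclusion.** The concern holds as an error of denominator and labelling. It is not a slip of arithmetic, since every stated figure reproduces. The firm consequence is for sensitivity: 400 enrolled deliver 194 positives only if at least about 69% have surgery (77% if dropout is separate), and power falls to about 74% and 66% at surgery rates of 60% and 50%. The specificity shortfall (74%, 67%, 59% and 49% at f = 0.8, 0.7, 0.6 and 0.5) is conditional on the literal reading of the 4.4 exclusion.

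This rests on three assumptions: 80% power; a 70/30 split among operated patients; and, where unoperated patients count as negatives, that all of them are judged non-cancer. A positive share above 70%, which the protocol allows for, would ease the positive group and tighten the pathology-verified negatives. The actual surgery rate is unknown, so the documents show an unsupported total and not a demonstrated loss of power. If the 900 is binding, the rates needed are about 31–34% for positives and 40–44% for pathology-verified negatives.

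**What to change.** 1. In 3.2.1.2, either label 278 and 360 as patients with a usable reference result, and 400 as that number before dropout, or state an assumed surgery proportion and divide by it. Then restate the total, or the expected group sizes and power at the planned enrolment. State the power used.
2. Reconcile the negative definition in 3.1.2, 3.2.1.2 and 4.4 with the 4.4 exclusion of patients without follow-up pathology. Base the negative share on the reconciled rule.
3. Reconcile 400 with the 900 implied by three sites of 300, and say which number governs enrolment for the clinical comparison.

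The cost is protocol wording and one short calculation. If the site minimum is made binding, it may cover the difference without further recruitment.
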